13.3.12 EQ-5D 5L Descriptive System

For each EQ-5D-5L dimension the proportion of subjects reporting no, slight, moderate, severe, and extreme/unable to perform activity will be summarized descriptively at each timepoint.

For the double-blind period, EQ-5D-5L descriptive system will be summarized at double-blind Baseline and double-blind Weeks 6, 14, and 26.

For the open-label period, EQ-5D-5L descriptive system will be summarized at open-label Baseline and open-label Week 12.

13.3.13 Pareto Classification of Health Change

Change from Baseline in EQ-5D 5L health state will be assessed with the Pareto classification of health change (PCHC) method. Using this methodology, at each post-Baseline visit, each EQ-5D health state will be classified into one of four categories, relative to the Baseline health state:

- Improved = improved on at least one dimension and not worsened on any other dimension
- Mixed = improved on at least one dimension and worsened on at least one other dimension
- No change = no changes in any dimension
- Worsened = deterioration on at least one dimension and no improvement on any other dimension

For the double-blind period, the proportion of subjects in each PCHC category will be summarized descriptively at the double-blind Weeks 6, 14, and 26.

For the open-label period, the proportion of subjects in each PCHC category will be summarized descriptively at the open-label Week 12.

14 SAFETY ANALYSES

The safety endpoints for this study are as follows:

- Treatment-emergent adverse events (TEAEs)
- Serious adverse events (SAEs)
- Withdrawals due to adverse events (AEs)
- Potentially clinically important changes in other safety assessments
- Global Clinician Assessment of Suicidality (GCAS) score

- Mini-Mental State Examination (MMSE) score
- Extrapyramidal Symptom Rating Scale A (ESRS-A) score

For the open-label period, safety data will be summarized for the Open-label Safety Analysis Set. The following summaries will be provided:

1. all subjects combined;
2. by randomization status (not randomized and randomized);
3. by final dose level (20 and 34 mg) of open-label pimavanserin administered during the open-label period.

For the double-blind period, safety data will be summarized for the Double-blind Safety Analysis Set. The following summaries will be provided:

1. by treatment group (placebo and pimavanserin)
2. by dose level (20 and 34 mg) of pimavanserin administered during the double-blind period for the pimavanserin group.

14.1 Adverse Events

All Adverse events (AEs) will be coded using MedDRA version 20.0 or newer.

An AE (classified by preferred term) will be considered a treatment emergent AE (TEAE) if the onset date was on or after the date of first dose of open-label pimavanserin and up to 30 days past the last dose of study drug. AEs reported on Day 1 based on open-label Baseline (pre-dose) findings (e.g. clinically significantly abnormal vital signs, laboratory test results, or electrocardiogram parameters) will not be considered as TEAEs.

Each TEAE will be assigned to either the open-label or double-blind period based on the onset date. For randomized subjects, if the onset date was on or after the date of first dose of double-blind study drug, the TEAE will be assigned to the double-blind period. All other TEAE will be assigned to the open label period.

The event counts and the number and percentage of subjects reporting TEAEs will be tabulated by SOC and preferred term; and, by SOC, preferred term, and maximum severity. If more than 1 AE occurs with the same preferred term for the same subject, the subject will be counted only once for that preferred term using the most severe occurrence for the

summarization by severity. In addition, the event counts and the number and percentage of subjects with TEAEs classified by the Investigators as related to the study drug, with most frequently reported TEAEs (preferred terms reported by $\geq 5\%$ of subjects overall for the open-label period and $\geq 5\%$ of subjects in either treatment group for the double-blind treatment period), with treatment emergent serious AEs, with fatal AEs (i.e. events that cause death), and with TEAEs leading to discontinuation of study drug will be summarized by SOC and preferred term. The display in these tables will be sorted alphabetically by SOC and then by descending subject frequency for the preferred terms using combined counts from both groups within each SOC. The event counts and the number and percentage of subjects with any TEAEs will also be tabulated by preferred term without SOCs. This table will be sorted by descending subject frequency using combined counts from all subjects.

An AE listing by subject will display all events in the open-label period and in the double-blind period, including those which are not treatment-emergent, and will include the verbatim term in addition to the MedDRA SOC and preferred term. This listing will also include all relevant eCRF data associated with the event: e.g. study period, date of onset, date resolved, study dose level at AE onset, severity, frequency, outcome, relationship to study drug, action taken with study drug, and required therapy. When a date is presented, the study day associated with the date will also be displayed. If the onset date is prior to, or during, the open-label period, the study day will be calculated relative to the date of first dose of open-label pimavanserin; if the onset date is during the double-blind period, the study day will be calculated relative to the date of first dose of double-blind study drug. Separate listings will be presented for subjects with SAEs, subjects with AEs leading to discontinuation and subjects with fatal AEs (if any). In these listings, an indicator for treatment-emergent events will also be included.

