NPI-NH psychosis score responder analyses also demonstrate the significant and clinically relevant treatment effect of pimavanserin 34 mg compared with placebo in subjects with ADP. Furthermore, defining responder as either a 30% or greater improvement or a 50% or greater improvement from Baseline NPI-NH psychosis score showed a significantly greater proportion of responders in the pimavanserin group (Table 1–2).

Table 1–2 NPI-NH Psychosis Score Percent Responder Analysis – Full Analysis Set – Week 6 (Day 43)

Treatment Group (% Responder)	Percent Improvement from Baseline				
	≥20%	≥30%	≥50%	≥75%	100%
Pimavanserin 34 mg	58.6%	55.2%	50.6%	27.6%	12.6%
Placebo	46.2%	37.4%	34.1%	16.5%	9.9%
p-value for test of group difference	0.0937	0.0159	0.0240	0.0656	0.5514

Source: ACP-103-019 Clinical Study Report

Note: Missing values were imputed as non-response

With respect to safety, pimavanserin appeared to be well-tolerated with no new safety observations in this elderly and frail patient population compared to the pimavanserin PDP safety database. An equal number of post-randomization deaths were reported: 4 deaths in the pimavanserin group and 4 in the placebo group.

There were more SAEs reported in pimavanserin group (16.7%) than in the placebo group (11.0%). A review of individual SAEs revealed a similar distribution of Medical Dictionary for Regulatory Activities (MedDRA) preferred terms between the two treatment groups with no clusters or common underlying mechanisms identified. However, there were fewer

discontinuations due to AEs in the pimavanserin group (8.9%) compared with the placebo group (12.1%).

The most frequently reported AEs in the pimavanserin group were fall (23.3%), urinary tract infection (22.2%), and agitation (21.1%). Agitation was reported more often in the pimavanserin group than in the placebo group.

The mean change from baseline in the QTc interval in subjects treated with pimavanserin was 9.4 ms at 12 weeks (Day 85) with no significant outliers reported at Day 85 (>500 ms or $\Delta \geq 60$ ms). One subject in the pimavanserin group and one subject in the placebo group had a $\Delta \geq 60$ ms at Day 15. Each subject continued in the study.

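### SAP 14.1 assigns adverse events to a period by onset date alone, so an event that began open-label but led to discontinuation or death during double-blind treatment is absent from the by-arm double-blind term-level tables

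*SAP*

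**What the plan says.** SAP 14.1 fixes the study period of every treatment-emergent AE (TEAE) from one date: "Each TEAE will be assigned to either the open-label or double-blind period based on the onset date". For a randomized subject the event counts as double-blind "if the onset date was on or after the date of first dose of double-blind study drug". Everything else goes by default the other way: "All other TEAE will be assigned to the open label period".

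The same section then defines the outcome tables, among them those for subjects "with fatal AEs (i.e. events that cause death), and with TEAEs leading to discontinuation of study drug will be summarized by SOC and preferred term". No different period rule is given for them.

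SAP 14 sets the layouts. Open-label safety is shown for all subjects, by randomization status and by final dose. Double-blind safety is shown by treatment group. Withdrawal because of an AE is one of the safety endpoints listed there.

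Four other provisions matter:

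- Protocol 7.2.2.1 gives an AE a new start date when its severity worsens significantly and lastingly, and closes a record when severity changes.
- SAP 6.2 tabulates double-blind discontinuation reasons, including Adverse event and Death. The general convention in SAP 5.1.2 makes this a by-arm table.
- SAP 13.2 tabulates the reasons again, explicitly by arm, with the same two rows.
- SAP 14.1 requires separate listings of AEs leading to discontinuation and of fatal AEs. SAP 5.1 generally sorts listings by randomized group.

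**The concern.** Every randomized subject has already had 12 weeks of pimavanserin, so some enter the double-blind period with an AE in progress. An onset rule suits general incidence, because it asks what started after randomization. It does not suit a table whose subject is an outcome, namely stopping the drug or dying, because that outcome can fall in a later period than the onset.

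A subject who completed the open-label period, was randomized, and later stopped double-blind drug for a persistent open-label-onset event is therefore shown in the term-level tables as an open-label discontinuation, under neither arm. Two outputs can then give different by-arm counts for the same safety endpoint, and the SAP does not say which governs or ask for them to be reconciled. The same rule can leave a death without an arm in the fatal-event table. That matters in a population for which the protocol itself (1.3.1) cites a boxed warning on mortality.

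**Working it through.** The plan states no figure on this point, so there is none to reproduce. The check follows a case through the planned outputs and then illustrates the possible size.

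**Step 1. Trace the case.** Take a randomized subject whose AE starts in open-label Week 10, continues at the same severity, and leads to stopping study drug in double-blind Week 6.

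| Output | Does the case appear? | By arm? | SOC and preferred term? |
|---|---|---|---|
| Double-blind TEAEs leading to discontinuation (SAP 14.1) | No; onset precedes first double-blind dose | – | – |
| Open-label TEAEs leading to discontinuation (SAP 14, 14.1) | Yes, in the randomized column | No | Yes |
| Double-blind disposition (SAP 6.2) | Yes, as Adverse event | Yes | No |
| Key secondary reason table (SAP 13.2) | Yes, as Adverse event | Yes | No |
| Listing of AEs leading to discontinuation (SAP 14.1) | Yes | Sorted by arm | Yes, but not summarized |

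No summary table gives both arm and term.

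**Step 2. The fatal variant.** If the subject leaves because of death, SAP 6.2 and 13.2 count it by arm. If the subject withdraws for another reason and then dies of an event with open-label onset, the recorded reason need not be Death. The event is also outside the double-blind fatal table. The case could then be in no by-arm summary table, only in listings.

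**Step 3. How far re-dating closes the gap.** An event that worsens significantly after randomization should get a new start date and so become a double-blind event. An unchanged, persistent event does not. Severity has three grades ending at severe (Protocol 7.2.1), and fatal is an outcome rather than a grade (Protocol 7.2.2.5). An event already severe in the open-label period therefore has no higher grade to trigger a new record.

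**Step 4. Illustrative size.** Let p be the share of randomized subjects with an open-label-onset AE in progress at randomization. Let q be the chance that it ends double-blind treatment without being re-dated. Neither is in the documents; both are assumptions. With the planned 89 per arm (Protocol 9.3), omitted subjects per arm = 89 × p × q. For example, 89 × 0.10 × 0.05 = 0.45. Entries are pimavanserin / placebo:

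| p | q 5% / 5% | q 10% / 5% | q 20% / 5% | q 5% / 10% |
|---|---|---|---|---|
| 5% | 0.22 / 0.22 | 0.45 / 0.22 | 0.89 / 0.22 | 0.22 / 0.45 |
| 10% | 0.45 / 0.45 | 0.89 / 0.45 | 1.78 / 0.45 | 0.45 / 0.89 |
| 20% | 0.89 / 0.89 | 1.78 / 0.89 | 3.56 / 0.89 | 0.89 / 1.78 |
| 30% | 1.33 / 1.33 | 2.67 / 1.33 | 5.34 / 1.33 | 1.33 / 2.67 |

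The arm difference in percentage points is 100 × p × (q on pimavanserin − q on placebo). Across p = 5% to 30% it is zero in the first scenario, about 0.2 to 1.5 in the second, 0.8 to 4.5 in the third, and about 0.2 to 1.5 the other way in the fourth. Randomization balances p in expectation, so any imbalance rests on q.

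**Step 5. Do the documents inform the direction?** Protocol 1.3.2 gives Phase 2 AE discontinuations of 8.9% on pimavanserin and 12.1% on placebo, which correspond to 8 of 90 and 11 of 91 (Fisher p = 0.63), and 4 deaths in each group. Those subjects were newly starting treatment. The figures do not describe events carried across a randomized withdrawal.

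**The case against.** The strongest reply is that little is actually hidden. The endpoint's by-arm totals are in SAP 6.2 and 13.2 whatever the onset date. The listings show each case with its preferred term. A discontinuation event in the randomized column of the open-label table must in principle have ended double-blind treatment, so it can be spotted. Re-dating moves worsening events into the double-blind period, and an event that turns fatal will often have worsened first. Table specifications sit in a separate document (SAP 1) that may handle this. An outcome-date rule would also show under placebo some events that began on pimavanserin.

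Most of this stands and limits the point. It does not remove it. Totals without terms do not show what subjects withdrew for. Listings leave the reader to rebuild a safety summary by hand. Re-dating misses unchanged events and those already severe. The SAP itself states the onset rule without exception. The placebo attribution is a real trade-off, which a flag makes visible.

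Two stronger readings are tempting. A reader might infer that the omission falls more on pimavanserin and flatters it, because a drug-caused event may persist where the drug continues and fade where it stops. That is possible, but no passage shows it, and many intolerant subjects may have left before randomization. A reader might also size the loss as a fixed share of the endpoint. Phase 2 rates applied to 89 per arm give 0.089 × 89 = 7.9 and 0.121 × 89 = 10.8 withdrawals. An assumed 10% to 30% share gives 0.8 to 2.4 on pimavanserin and 1.1 to 3.2 on placebo. The share is not in the documents, the rates come from a different design, the result leans towards placebo, and the arm totals are not lost in any case.

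**Conclusion.** The point holds in limited form. As written, SAP 14.1 keeps an open-label-onset, not re-dated event that leads to double-blind discontinuation or death out of every by-arm term-level table. Three things are lost: the by-arm SOC and preferred-term summary of such events, agreement between the TEAE and disposition counts for AE withdrawals, and possibly the arm attribution of deaths after withdrawal for another reason.

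Size and direction cannot be derived from the documents. The illustration's 0.2 to 5.3 subjects per arm rests entirely on assumed p and q, and its direction reverses with them. The conclusion also assumes that the separate table specifications add no outcome-date rule. Efficacy analyses are unaffected. The correction is worth making because outcome counts may be small and the rule is best settled before unblinding.

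**What to change.** Keep the onset rule in SAP 14.1 for general TEAE incidence. Add two by-arm tables for the Double-blind Safety Analysis Set, by SOC and preferred term, regardless of AE onset date:

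- (a) all AEs leading to study-drug discontinuation on or after the first double-blind dose;
- (b) all fatal AEs with death on or after the first double-blind dose.

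Flag events with open-label onset in both. Reconcile (a) with the Adverse event counts in SAP 6.2 and 13.2, and explain any differences. Some may be legitimate: SAP 13.2 restricts its relapse row to adjudicated relapses, and its population need not match the safety set.

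The cost is a little extra programming: last-dose date, action taken and AE outcome are already used in SAP analyses or listings. The drawback is that some events that began on open-label pimavanserin will be shown, flagged, under placebo.

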Assessment for response criteria					X	X
Assessment for concomitant medications	X	X	X	X	X	X
Global Clinician Assessment of Suicidality	X	X	X	X	X	X
Extrapyramidal Symptom Rating Scale A		X				X
Assessment for adverse events	X	X	X	X	X	X
Pharmacokinetic sample collection ^g		X			X	X
Pharmacogenomic sample collection ^h		X				
Drug dispensation		X	X	X	X	X ⁱ
Drug return and accountability			X	X	X	X
Randomization						X

Footnotes for Table S–1 on next page

Abbreviations: CT=computed tomography; MRI=magnetic resonance imaging; SAPS-H+D=Scale for the Assessment of Positive Symptoms, Hallucinations and Delusions subscales

Note: All efforts should be made to complete each visit in a single day. In the event of a split visit, the CGI-S/CGI-I and the SAPS H+D must be completed on the same day.

Note: When a subject is found to be appropriate for discontinuation from the trial, the visit during which this is determined should immediately be converted to an ET visit (as described in [Table S–2](#)) and all procedures and assessments listed in the schedule of events for the ET visit (Week 38/EOT; Visit 17/ET) should be completed (additional details provided in [Section 4.4](#)). Safety follow-up should be completed as scheduled.

For additional details on study procedures, see [Section 6](#).

- a Visit 6 (Week 12) will serve as both the final visit of the open-label period and the Baseline visit of the double-blind period ([Table S-2](#)).
- b A non-contrast brain MRI or non-contrast head CT will be completed if the subject has not had a CT or MRI scan completed (a) within the past 3 years AND (b) during or subsequent to the onset of dementia.
- c The ECG will be completed in triplicate at Visit 1 (Screening). A single ECG will be completed at all other visits.
- d A pregnancy test (serum at Visit 1 and urine at all other visits) is only required for women of childbearing potential. If urine cannot be obtained in women of childbearing potential, a serum pregnancy test should be done.
- e The CGI-I should be scored relative to Visit 2, the subject's open-label Baseline.
- f The ZBI should only be administered to study partners/caregivers who are family members.
- g Pharmacokinetic samples will also be collected, if possible, at any ET visit ([Table S-2](#)) or the visit immediately following any SAE or following an AE leading to discontinuation.

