- h A separate informed consent (and assent, if applicable) must be given for the pharmacogenomic component of the study. This consent may be obtained at any time during the study. If informed consent is given in time for sample collection at Visit 2, a pre-dose sample should be collected at Visit 2. If informed consent for pharmacogenomics is not given in time for sample collection at Visit 2, a sample may be collected any time after informed consent for pharmacogenomics is given.
- i Blinded study drug will be dispensed after randomization at Visit 6 (Week 12).

Table S–2 Schedule of Assessments for ACP-103-045: Double-blind Period

Visit week	13	14	16	18	20	22	24	26	30	34	38/EOT	42
Allowable visit window (# days)	±3	±3	±3	±3	±3	±3	±3	±3	±7	±7	+7	+3
Visit Number	7	8	9	10	11	12	13	14	15	16	17/ET	18
Visit Type (Clinic [C] or Telephone [T])	C	C	C	C	T	C	T	C	C	C	C	T
Mini-Mental State Examination	X	X	X	X		X		X	X	X	X	
Physical and neurological examinations						X					X	
Vital signs and weight	X	X	X	X		X		X	X	X	X	
12-lead electrocardiogram				X				X			X	
Clinical laboratory tests				X				X			X	
Pregnancy test ^a								X			X	
SAPS-H+D	X	X	X	X		X		X	X	X	X	
Clinical Global Impression-Improvement ^b	X	X	X	X		X		X	X	X	X	
Clinical Global Impression-Severity	X	X	X	X		X		X	X	X	X	
Zarit Burden Interview ^c				X				X			X	
Karolinska Sleepiness Scale				X				X			X	
EQ-5D-5L				X				X			X	
Assessment for protocol-defined relapse criteria	X	X	X	X	X	X	X	X	X	X	X	
Assessment for concomitant medications	X	X	X	X	X	X	X	X	X	X	X	X
Global Clinician Assessment of Suicidality	X	X	X	X	X	X	X	X	X	X	X	
Extrapyramidal Symptom Rating Scale A	X	X	X	X		X		X	X	X	X	
Assessment for adverse events	X	X	X	X	X	X	X	X	X	X	X	X
Pharmacokinetic sample collection ^d	X					X					X	
Drug dispensation		X	X	X		X		X	X	X		
Drug return and accountability	X ^e	X	X	X		X		X	X	X	X	

Footnotes and abbreviations for Table S-2 on next page

Abbreviations: EOT=end-of-treatment; ET=early termination; SAPS-H+D=Scale for the Assessment of Positive Symptoms, Hallucinations and Delusions subscales

For additional details on study procedures, see [Section 6](#).

Note: All efforts should be made to complete each visit in a single day. In the event of a split visit, the CGI-S/CGI-I and the SAPS H+D must be completed on the same day.

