5.2.2 Double-blind Baseline

Double-Blind Baseline is defined as the last non-missing assessment, including those from repeated and unscheduled measurements, on or before the date of first dose of double-blind study drug.

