5.3 Analysis Visit Windows

5.3.1 Open-label Period

Efficacy, safety and pharmacokinetic assessments for the open-label (OL) period will be summarized by analysis visit as presented in [Table 3](#). For exploratory efficacy endpoints and MMSE, assessments more than 14 days after last dose of study drug will be assigned an analysis visit but will not be selected for the by-visit analyses.

Table 3 Analysis Visit Windows for the Open-label Period

Study Visit	Analysis Visit	Target OL Study Day ^a	Study Day Interval
Week 0	OL Baseline	1	≤1
Week 2	OL Week 2	15	2 to 21
Week 4	OL Week 4	29	22 to 42
Week 8	OL Week 8	57	43 to 70
Week 12	OL Week 12	85	71 to 98 (or day of first dose of double-blind study drug ^b)

^aDerivation of open-label study day is described in [Section 5.1.1](#). Open-label study day 1 is the date of first dose of open-label pimavanserin.

^bFor subjects who are randomized in the double-blind period.

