5.3.2 Double-blind Period

Efficacy, safety, and pharmacokinetic assessments for the double-blind (DB) period will be summarized by analysis visit as presented in Table 4. For exploratory efficacy endpoints and MMSE, assessments more than 14 days after last dose of study drug will be assigned an analysis visit but will not be selected for the by-visit analyses.

Table 4 Analysis Visit Windows for the Double-Blind Period

Study Visit	Analysis Visit	Target DB Study Day ^a	Study Day Interval
Week 12	DB Baseline	1	≤1
Week 13	DB Week 1	8	2 to 11
Week 14	DB Week 2	15	12 to 21
Week 16	DB Week 4	29	22 to 35
Week 18	DB Week 6	43	36 to 49
Week 20	DB Week 8	57	50 to 62
Week 22	DB Week 10	71	63 to 77
Week 24	DB Week 12	85	78 to 91
Week 26	DB Week 14	99	92 to 112
Week 30	DB Week 18	127	113 to 140
Week 34	DB Week 22	155	141 to 168
Week 38	DB Week 26	183	169 to 197

^aDerivation of double-blind study day is described in [Section 5.1.2](#). Double-blind study day 1 is the date of first dose of double-blind study drug.

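### SAP 14.1 has no pre-dose exception at Week 12, so an adverse event from a pre-dose finding dated on the first blinded dose day counts as double-blind, placebo included

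*SAP*

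**What the plan says.** **Adverse events.** SAP 14.1 contains two rules.

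- At the start of open-label treatment, "AEs reported on Day 1 based on open-label Baseline (pre-dose) findings" are not counted as TEAEs. Abnormal vital signs, laboratory results and ECG parameters are the examples given.
- At the start of blinded treatment, "if the onset date was on or after the date of first dose of double-blind study drug", then "the TEAE will be assigned to the double-blind period". All other TEAEs go to the open-label period. There is no pre-dose exception.

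**The visit.** Protocol Table S-1, footnote a: "Visit 6 (Week 12) will serve as both the final visit of the open-label period and the Baseline visit of the double-blind period". The same table schedules vital signs, ECG, laboratory tests and physical and neurological examinations at Week 12. Footnote i has blinded drug handed out at that visit, once the subject has been randomized.

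**Measurements.** SAP 5.2.2 takes double-blind Baseline as the last non-missing assessment "on or before the date of first dose of double-blind study drug". SAP Table 3 closes the open-label Week 12 window at day 98 "or day of first dose of double-blind study drug" for randomized subjects. SAP Table 4 gives the Week 12 visit a target of double-blind study day 1, and its footnote states: "Double-blind study day 1 is the date of first dose of double-blind study drug".

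**The concern.** The SAP treats one calendar day in two ways. A Week 12 measurement taken on the first blinded dose date is a pre-dose value in the laboratory, ECG and vital sign tables. An adverse event written up from that same measurement is a double-blind event in the TEAE tables.

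SAP 4.3 analyzes double-blind safety by the treatment actually received in that period. For a subject randomized to placebo, an event that arose on open-label pimavanserin is then reported as a placebo event. The safety objective (Protocol 2.4, SAP 2.4) is pimavanserin compared with placebo, so the double-blind TEAE tables should not carry events that precede blinded treatment.

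**Working it through.** No stated figure is in dispute, so the main check is to trace the rule.

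**Step 1: which events are caught.**

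- Onset date before the first blinded dose date: open-label.
- Event found at the Week 12 visit, blinded dosing begun on a later day: open-label.
- Onset date equal to the first blinded dose date, finding made before the dose: the SAP 14.1 condition is met, so the event is double-blind.
- Onset date equal to or later than the first blinded dose date, event after the dose: double-blind, correctly.

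Only the third case is wrong. Protocol 7.2.2.1 records the start of an event as a date and specifies no time, so clock time cannot separate the third case from a same-day post-dose event.

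**Step 2: does another section supply the exception?** SAP 5.4.2 deals only with missing or incomplete onset dates. No other section addresses it.

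**Step 3: where the events land.** Randomization is 1:1 (Protocol 5.1.5), so about half fall under placebo and half under pimavanserin.

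**Step 4: scale.** The planned arm size is 89 (Protocol 9.3). It reproduces from the protocol's assumptions. With exponential relapse (60% and 35%) and dropout (25%) over 26 weeks, the event probabilities are 0.533 and 0.307, mean 0.420, and 75 / 0.420 = 178.6, against 178 stated.

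The documents give no rate for pre-dose Week 12 events. Let q be the assumed share of subjects with one:

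- q = 1%: 0.01 × 89 = 0.9 per arm
- q = 3%: 0.03 × 89 = 2.7 per arm
- q = 5%: 0.05 × 89 = 4.5 per arm

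**Step 5: effect on a comparison.** Take a hypothetical incidence of 10% on drug and 5% on placebo, and add q to both:

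- q = 0: difference 5 points, ratio 10 / 5 = 2.0
- q = 1%: 11% and 6%, difference 5 points, ratio 1.8
- q = 3%: 13% and 8%, difference 5 points, ratio 1.6

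Simple addition ignores subjects who already have another qualifying event and are counted once. If the two are independent, each incidence p becomes p + q(1 − p), and the difference is multiplied by (1 − q). At q = 3% that is 5 × 0.97 = 4.85 points, which is still essentially unchanged. For a single preferred term the relevant q is smaller, because the findings spread over many terms.

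**Step 6: display threshold.** The double-blind frequent-TEAE table lists preferred terms reached by at least 5% of either group. 0.05 × 89 = 4.45, so 5 subjects are needed. One misassigned event takes a term from 4/89 = 4.5% to 5/89 = 5.6%.

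**The case against.** **The case for leaving the rule alone.** The open-label Day 1 exception decides whether an event is treatment-emergent at all. At Week 12 the subject has had 12 weeks of drug, so the event is a TEAE either way and only its period label changes. Safety is summarized descriptively, with no planned adverse event test or risk ratio. The SAP 14.1 listing shows study period, onset date, study day and dose level at onset, so double-blind Day 1 events can be found.

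This bounds the importance of the point. It does not make the label right: the period label decides which column of the double-blind table the event enters, and SAP 5.2.2 and Table 3 place the underlying measurement on the other side of the line.

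**Stronger readings that the documents do not support.**

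- *Every event found at Week 12 is misassigned.* Assignment is by onset date, not detection date. How often the first blinded dose falls on the visit day is also not stated. Table 4 targets it, but Protocol 5.1.3, which has the first dose of study drug given in the clinic, does not say whether that covers the first blinded dose.
- *The rule biases the comparison against one arm or erases the risk difference.* Under 1:1 randomization both arms gain about equally. The incidences and their ratio move, and the expected difference essentially does not.
- *Early placebo events fall within a 30-day open-label attribution window.* The 30 days in SAP 14.1 run from the last dose of study drug, which for a randomized subject is the last double-blind dose. It is an end-of-treatment capture window.
- *A TEAE table restricted to onset after double-blind Day 30 would help.* Relapsers stop study drug (Protocol 3.4). Under exponential relapse at the protocol's rates, 1 − 0.40^(30/182) = 14% of placebo and 1 − 0.65^(30/182) = 7% of pimavanserin subjects relapse by Day 30. Such a table would compare differentially selected groups.

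**Conclusion.** The point holds as an internal inconsistency in a stated rule. Followed as written, SAP 14.1 misclassifies events that come from pre-dose Week 12 findings and are dated on the first blinded dose day, and it reports about half of them under placebo.

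The effect is probably small and its size is unknown; the 1% to 5% range and the 10% against 5% example are assumptions. What can be said is the direction: double-blind TEAE incidence is inflated in both arms by about the same amount, the ratio is pulled toward 1, and a preferred term near the threshold can enter the frequent-TEAE table. The primary and key secondary efficacy analyses are untouched.

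**What to change.** Add one sentence to SAP 14.1, after the period-assignment rule: *adverse events with onset on the date of the first double-blind dose that are based on double-blind Baseline (pre-dose) findings are assigned to the open-label period.* This mirrors the existing open-label Day 1 sentence and agrees with SAP 5.2.2 and Tables 3 and 4.

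Because no onset time is specified, these events have to be identified by their link to a Week 12 assessment, as the open-label Day 1 exception already requires. That should be done before unblinding. Same-day events that do not rest on a pre-dose finding stay in the double-blind period.

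The cost is one SAP sentence and a short programming and data review step. No protocol amendment, new data collection or extra table is needed.
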